### **Project status**

Study recruitment is complete. We have extracted and analyzed data for the primary outcome. We have not yet extracted or analyzed data for any secondary outcomes.

In August, 2021, on the advice of our clinical collaborators, we intended to change the secondary outcome time frame for flu diagnosis to be measured on April 30, 2022 rather than March 31, 2022. We also intended to change the secondary outcome time frame for flu complications to be measured on July 31, 2022 rather than March 31, 2022. These dates are consistent with a study timeline we submitted to the NIH in August 2021. However, we neglected to make these changes to our preregistration on [clinicaltrials.gov](https://clinicaltrials.gov). The original version of this Statistical Analysis Plan included the previous secondary outcome dates, which were copied from the [clinicaltrials.gov](https://clinicaltrials.gov) preregistration.

Additionally, our earlier Statistical Analysis Plan version did not include a preregistered time frame for 2022-23 flu shots. We intend to measure this outcome as of December 31, 2022, to be consistent with the date we measured flu shots in the 2021-22 flu season (December 31, 2021).

This modified Statistical Analysis Plan and our [clinicaltrials.gov](https://clinicaltrials.gov) page now reflect our corrected secondary outcome time frames and our estimated study completion date (December 31, 2022, the date we will measure 2022-23 flu shots). The secondary outcome time frames, the clarified time frame for 2022-23 flu shots, and this Project status section are the only changes from the original Statistical Analysis Plan.

### **Planned Analyses**

#### ***Primary Outcome***

Flu vaccination at appointment [ Time Frame: 3 days after patient is randomized ]

**Question 1:** Can lottery incentives increase flu vaccination rates better than equivalent-value cash payouts, active control messages, or no messages?

*Analysis 1a (Confirmatory):* We will test the hypothesis that patients who are sent messages with promise of an official state lottery ticket if they get vaccinated (patients randomized to message group 1) will exhibit improved flu vaccination rates compared with patients who are sent messages offering a certain \$1 cash payout if they get vaccinated (group 2).

*Analysis 1b (Confirmatory):* We will test the hypothesis that patients who are sent messages with promise of an official state lottery ticket if they get vaccinated (patients randomized to message group 1) will exhibit improved flu vaccination rates compared with patients who are sent active control messages (group 3).

*Analysis 1c (Confirmatory):* We will test the hypothesis that patients who are sent messages with promise of an official state lottery ticket if they get vaccinated (patients randomized to message group 1) will exhibit improved flu vaccination rates compared with patients who are sent no messages (group 4).

For analyses 1a through 1c, we will run an OLS regression, with a dummy variable coding for no message (group 4), active control message (group 3), cash (group 2), or state lottery (group 1).

**Question 2:** Do active control messages encouraging flu shots at an upcoming appointment increase flu vaccination rates?

*Analysis 2 (Confirmatory):* We hypothesize that patients who are sent active control messages encouraging them to get a flu shot without any associated incentives (group 3) will be more likely to get vaccinated than those in the no-contact control group (group 4). To assess this hypothesis, we will employ OLS regression with a categorical predictor variable coding for group (group 3 vs. group 4).

**Question 3:** Do small cash incentives increase flu vaccination more than active control messages or no messages?

*Analysis 3a (Exploratory):* We will test whether patients sent text messages promising small cash incentives in exchange for vaccination (group 2) are more likely to get vaccinated than those who are sent active control messages (group 3).

*Analysis 3b (Exploratory):* We will test whether patients sent text messages promising small cash incentives in exchange for vaccination (group 2) are more likely to get vaccinated than those who are not sent any messages (group 4).

For Analyses 3a and 3b, we will run one OLS regression, with a dummy variable coding for no message (group 4), simple message (group 3), or cash (group 2).

We will not correct for multiple comparisons in the analyses above, as adjustment is not appropriate for individual testing, where each result must be statistically significant to reject its associated

individual null hypothesis (Rubin, 2021). That is, each significant result is an indicator of a specific null hypothesis rejection and has no direct bearing on the success of other hypotheses or the overall study.

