Based on our power calculation, we need at least 9,806 patients in each arm of the study. Therefore, for each additional 9,806 patients beyond our minimum projected sample size of 39,224, we will add an additional arm.

If our sample is sufficiently high to run any of Arms 6-9, we will obtain a Small Games of Chance (SGOC) license, and we have already initiated this process in anticipation of running these arms.

Because this intervention is timed to the 2021-22 flu season, the intervention period will begin ~9/1/21. In the active conditions, participants will receive SMS text messages, phone, and/or letter reminding them of their upcoming appointment (3 days prior to the appointment, and again 1 day prior to the appointment) and telling them to ask for their flu shot. In the incentive conditions, to comply with state and federal regulations, participants will be told of a possible "cash bonus" and that they must reply to learn more about the incentive details. Participants will be informed that receipt of incentives is contingent upon documented vaccination in the electronic health record. We will also obtain data on cohabitants of the experimental subjects (anticipated n=80,000).

The primary outcome will be whether the patient was vaccinated at the scheduled appointment, as recorded in the EHR. A secondary outcome will be flu vaccination within 7 days of receiving the intervention. Additional secondary outcomes will include pre-commitment via "Y" response to the initial text, vaccination during the subsequent flu season (to assess if behavior is maintained absent subsequent incentives); rates of flu diagnoses (both using the most rigorous biological tests, "high confidence flu", and using broader criteria that also include diagnosis codes and treatment information, "likely flu"), rates of flu complications and other relevant healthcare utilization outcomes such as emergency department visits, hospitalizations, and insurance claims (for an expected ~40% of participants who are members of Geisinger Health Plan). We will also measure rates of flu vaccination, diagnoses, and complications by non-targeted household members who are likely to include older parents of patients and their spouses/partners. Finally, we will measure rates of COVID-19 vaccination in target participants and their household members.

Data Sources

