In order to identify patients in the primary target population, **Business Intelligence & Advanced Analytics** (BIAA), working with **Geisinger's Phenomics and Clinical Data Core** (PACDC), will provide a list of patients (including patient identifiers such as Medical Record Number) that meet our eligibility criteria.

We will also obtain contact information (address, phone number, email address) to message participants in the primary target population from BIAA & PACDC.

After the intervention is complete, we will obtain outcomes data for both target and household population groups from BIAA & PACDC. This will include data on patient flu vaccination, diagnosis of flu, diagnosis of flu-like symptoms, presence of flu-associated complications, hospital visits, emergency department visits, and COVID-19 vaccination status. This data set will additionally include patient characteristics that will be useful as analysis covariates, such as: age, patient primary care provider, and flu-related behavior and outcomes during previous flu seasons.

STUDY DATA DETAILS

Data Management Procedures and Confidentiality. All data will be electronic. Datasets with full identifying information will only be stored on Geisinger-managed, password-protected computers of the data brokers ([name] and [name]) for the purpose of linking datasets from different sources.

A limited data set containing dates of service and ZIP codes will be shared with any non-Geisinger collaborators (e.g., Additional Principal Investigator [name] and his team) under a Data Use Agreement (pending approval) in compliance with HIPAA's Privacy Rule, and using data security protocols reviewed and approved by the Geisinger Security Office, Privacy Office, and Information Technology department.

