### Power analysis

The study team planned to enroll at least 9,806 patients per study arm. Assuming a baseline vaccination rate of 50%, this sample would allow 80% power to detect a 2% absolute percentage-point difference, or a 4% relative difference, between any two groups.

In August, 2021, we completed an analysis of the anticipated number of eligible patients in the study. This analysis suggested that our sample would be large enough to run four study arms (i.e., we projected that we would enroll more than 39,224 participants, but fewer than 49,030, the number that would have been required to add a fifth arm). Therefore, we proceeded with running only the priority four pre-registered study arms, and we anticipate enrolling a total of at least 39,224 patients across those four groups.

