### Sample and Randomization

The sample includes patients who have an upcoming primary or specialty appointment where they can get a flu shot, and who, according to Geisinger's records, have not yet received a flu shot in the 2021–22 flu season. Patients are also age 18 or older, are not contraindicated for flu shots, and have an assigned Geisinger PCP. All patients are also eligible to receive text messages from Geisinger.

The four study groups include:

1. Pennsylvania (PA) Lottery Scratch-Off Financial Incentive - Participants in this arm receive a message stating that they will receive a PA lottery \$1 scratch-off ticket if they get a flu shot at an upcoming appointment. The message will mention that they could win \$5,000 (the top prize for the scratch-off game).
2. Certain Cash Payout Financial Incentive - Participants in this arm receive a message stating that they will receive \$1 in cash if they get a flu shot at an upcoming appointment.
3. Reminder / Active Control (No Financial Incentive) - Participants in this arm receive a message stating that they can get a flu shot at an upcoming appointment. These participants will not be offered a financial incentive for getting a flu shot.
4. No Intervention: No Treatment Control - No additional contact beyond standard Geisinger flu shot communications

Each day, the study team receives a list of eligible patients with flu-shot-eligible appointments in the upcoming 3 days. Patients with appointments in 3 days are randomized into the 4 groups described above. Those in groups 1-3 receive their first messages 3 days prior to their appointment.

All patients who are sent 3-day messages are sent 1-day messages, as long as they appear on the list of eligible patients the day prior to their appointment. There are two reasons patients may not appear in that list: 1) their appointment is rescheduled and they no longer have a flu-shot-eligible appointment scheduled on that date, or 2) Geisinger records are updated indicating the patient got a flu shot after randomization but before the 1-day reminder list is created, rendering the patient ineligible for a flu shot at their appointment.

In cases where a patient cancels their appointment or reschedules it for a different day, they are not sent a 1-day message.

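### The arm comparisons for the primary and 7-day vaccination outcomes leave out 2020-21 flu vaccination status, a cheap precision gain of unknown size that the plan misses without being in error

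*SAP*

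**What the plan says.** - **Primary outcome.** SAP, Planned Analyses, Primary Outcome: "For analyses 1a through 1c, we will run an OLS regression, with a dummy variable coding for no message (group 4", with further categories for groups 3, 2 and 1. Analysis 2 and Analyses 3a and 3b likewise use group terms only.
- **Checks.** SAP, Sensitivity analyses and robustness checks: the shared-address, message-receipt and logistic reruns repeat those models. The one covariate-adjusted arm comparison uses sex, binned age and their interactions.
- **7-day vaccination.** SAP, Secondary outcomes, applies the approaches of Analyses 1 to 3, so this model is also unadjusted.
- **Where 2020-21 status appears.** Only in SAP, Additional exploratory analyses, item 6, as a main effect and an interaction with arm.
- **Protocol, Data Sources.** The extract will hold characteristics "useful as analysis covariates, such as: age, patient primary care provider, and flu-related behavior and outcomes during previous flu seasons".
- **2022-23 vaccination.** The Protocol (Detailed Study Procedures) lists as a secondary outcome "vaccination during the subsequent flu season (to assess if behavior is maintained absent subsequent incentives"). SAP exploratory item 7 sets a measurement date but names no model.
- **Timing.** SAP, Project status: "We have extracted and analyzed data for the primary outcome". It then says "We have not yet extracted or analyzed data for any secondary outcomes". The revised time frames and that section itself "are the only changes from the original Statistical Analysis Plan", so item 6 was already planned.

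**The concern.** Last season's vaccination is an earlier measure of the same behaviour as the outcome, and item 6 itself expects some patients to be vaccinated every year. The plan adjusts for sex and age in a check but not for this variable, which it must obtain anyway.

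Item 6 does not fill the gap. It tests whether the arm effect differs by prior status. With ordinary dummy coding, each arm coefficient in that model refers to one prior-vaccination stratum and is not an average effect.

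Precision is what is at stake. Recruitment is complete, so narrower intervals can now come only from the analysis.

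**Working it through.** **Inputs.** From SAP, Power analysis: 9,806 per arm, 50% baseline, and "this sample would allow 80% power to detect a 2% absolute percentage-point difference". The documents state no alpha; two-sided 0.05 is assumed. The correlation of 2020-21 status with the outcome is not given either, so a range is used.

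**Step 1: reproduce the plan's figure.** Pooled two-proportion formula, with p1 = 0.50, p2 = 0.52 and mean 0.51:

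n = [1.960 × √(2 × 0.51 × 0.49) + 0.842 × √(0.50 × 0.50 + 0.52 × 0.48)]² / 0.02² = 9,806 per arm.

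This matches exactly, which supports the assumed alpha; a one-sided test would need 7,725. Four arms give 4 × 9,806 = 39,224, also as stated. The design meets its power with no covariate.

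**Step 2: effect of the covariate.** The unadjusted standard error is √[(0.2500 + 0.2496) / 9,806] = 0.714 percentage points. A baseline covariate multiplies it by √(1 − R²). Power is Φ(2 / SE − 1.96), with SE in points. For a binary covariate, R² = gap² × q(1 − q) / [p(1 − p)], where p is the overall rate, q the share previously vaccinated, and gap the difference in current vaccination between previously vaccinated and unvaccinated patients. At p = q = 0.5, R² = gap².

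| Assumed gap (points) | R² | SE (points) | SE reduction | Illustrative power | Detectable difference (points) |
|---|---|---|---|---|---|
| 0 | 0 | 0.714 | none | 80.0% | 2.00 |
| 10 | 0.01 | 0.710 | 0.5% | 80.4% | 1.99 |
| 20 | 0.04 | 0.699 | 2.0% | 81.6% | 1.96 |
| 30 | 0.09 | 0.681 | 4.6% | 83.6% | 1.91 |
| 40 | 0.16 | 0.654 | 8.3% | 86.4% | 1.83 |
| 50 | 0.25 | 0.618 | 13.4% | 89.9% | 1.73 |

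Nothing in the documents supports the last row. The power column shows scale on the design assumptions only.

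**Step 3: wider grid.** Take p from 30% to 50%, q from 30% to 70%, and gaps of 10 to 40 points.

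- Smallest gain: gap 0.10, q = 0.3, p = 0.5. R² = 0.01 × 0.21 / 0.25 = 0.0084, so the SE is 0.4% smaller.
- Largest gain: gap 0.40, q = 0.5, p = 0.3. R² = 0.16 × 0.25 / 0.21 = 0.190, so the SE is 10.0% smaller.

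**Step 4: gain over the sex-and-age check.** Steps 2 and 3 compare with a model that has no covariates. Suppose, for illustration, that sex and age explain 2% and adding prior status brings the total to 4%. The SE ratio is √(0.96 / 0.98) = 0.990, a 1.0% reduction instead of 2.0%.

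**Step 5: item 6 as written.** With half the sample in each prior-status stratum, the stratum-specific arm coefficient has SE 0.710 × √2 = 1.00 points at R² = 0.01 and 0.618 × √2 = 0.87 at R² = 0.25. Both are wider than the unadjusted 0.714. Averaging over the strata brings them back to 0.710 and 0.618.

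**Step 6: check for bias.** In simulations of four-arm trials (8,000 per setting, true average effect 2 points), the mean estimate was 1.99 to 2.01 points for the unadjusted, covariate-adjusted and stratum-averaged models alike.

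**The case against.** The strongest case against is that nothing here is wrong. Unadjusted OLS in a randomized trial of at least 39,224 patients, with an adjusted check, is an ordinary choice, and the sample size reproduces without a covariate. That stands.

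Three further points also stand:

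- **Size.** The documents give no predictive strength. It may be weak, because the sample is restricted to patients who "have not yet received a flu shot in the" 2021-22 season and the primary outcome concerns a single visit.
- **Timing.** The primary outcome is analysed. Appointments fall 3 days after randomization, so appointment-day vaccinations lie inside the 7-day window and that outcome is partly known too. Adding models now adds some analytic flexibility in a plan without multiplicity correction.
- **Item 6 outcome.** It says only that 2021-22 vaccination is modelled, so using it for the primary outcome means fixing the outcome as well as the averaging step.

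These points limit the remedy but do not remove the case for it. The covariate precedes randomization, has to be obtained anyway and costs one degree of freedom (or two, if missing records form a category). A labelled adjusted estimate beside the planned one replaces nothing.

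A reader might infer that the Protocol commits the trial to adjusting for prior vaccination. It does not: it describes the extract and calls such variables useful. Nor does exploratory item 7 choose against adjustment for 2022-23 vaccination; it is silent on the model.

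**Conclusion.** The omission is real, and it is a missed efficiency, not an error. The standard error would be about 0.4% to 10% smaller than with no covariates, assuming overall rates of 30% to 50%, 30% to 70% previously vaccinated, and gaps of 10 to 40 points. The increment over the sex-and-age model may be smaller. If prior status predicts weakly, the gain is negligible.

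A reader might take the table to mean that the trial is underpowered, or that adjustment would lift its confirmatory power towards 90%. The documents support neither. The stated 80% is met, the primary result is already in hand, and a post hoc estimate cannot restore confirmatory power. For 2022-23 vaccination no rate or target difference is given, so no power gain can be stated at all.

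**What to change.** Before secondary outcomes are extracted, add a few sentences to the SAP:

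1. **7-day vaccination.** Keep the planned unadjusted OLS model. Report beside it the same model plus 2020-21 vaccination status.
2. **Missing records.** Fix one rule for patients with no 2020-21 record: count them as not vaccinated, or give them their own category. Either rule leaves the arm contrast unbiased, because the status precedes randomization.
3. **OLS only.** Do not extend the adjustment to the logistic rerun, where it would change the odds ratio being estimated from marginal to conditional.
4. **2022-23 vaccination.** If arms are compared, use the same unadjusted and adjusted pair, so that the result can be set against the primary analysis.
5. **Primary outcome (optional).** Leave the preregistered result and the sex-and-age check unchanged. Fit item 6's model to vaccination at the appointment and also report the arm effects averaged over the prevalence of 2020-21 vaccination, labelled post hoc.
6. **Disclosure.** State that these additions were made after the primary results were known and that the 7-day window includes appointment-day vaccinations.

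The cost is some wording and slightly more analysis, with no new data. The downsides are that none of the added models is blind to the primary results, and that the gain may prove negligible.

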### **Sensitivity analyses and robustness checks**

Some patients lived at the same address, but we decided to randomize patients independently, without accounting for whether a household member was also in the study. Therefore, some patients may have been assigned to different groups from their household members. Alternatively, it is possible household members were assigned to the same group. Either possibility may affect the impact of our intervention (e.g., the same messages received by multiple household members may reinforce the message and strengthen the impact of the messages, while different messages could cause confusion and weaken the messages' effectiveness). To ensure findings do not depend on such interactions between patients residing at the same address, we will run a sensitivity analysis by removing all patients who share an address with another patient in the study and computing the same analyses listed above.

Recent work suggests that OLS regressions are appropriate in randomized experiments with binary outcome variables such as ours (Gomilla, 2021). However, as a robustness check, we will also run the regressions described above as logistic regressions instead of OLS regressions.

On 10/6/21, we realized that we had enrolled patients based on their age on the date of their appointment rather than their age on the date of randomization, when we sent the 3-day messages. There were 2 patients enrolled who turned 18 in the 3 days between enrollment and their appointment date. These patients were removed from the study and will be excluded from all analyses.

We will use an intent-to-treat approach for our statistical analyses, including all patients who were randomized. However, we will also run the analyses described above with the subset of patients who, according to text-message records from Twilio, received both 3-day and 1-day reminder messages. This robustness check will exclude patients who were randomized but were never sent messages for a variety of reasons (e.g., their phone numbers were inactive, they were on a do-not-contact list that the research team did not have access to prior to randomization). Additionally, we will exclude patients who were sent only a 3-day message, but who were not sent a 1-day message. We will also exclude a limited number of patients who received repetitions of the same message due to technical glitches outside the study team's control.

Finally, as an additional robustness check, we will run OLS regression analyses controlling for sex, binned age (18-24, 35-44, 45-54, 65+), and interactions among sex and age as covariates.

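### The both-messages robustness check has no defined comparator for contrasts with the no-message arm (1c, 2 and 3b)

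*SAP*

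**What the plan says.** The main analysis is not in dispute: "We will use an intent-to-treat approach for our statistical analyses, including all patients who were randomized" (SAP, Sensitivity analyses and robustness checks). The same paragraph then reruns the earlier analyses in "the subset of patients who, according to text-message records from Twilio, received both 3-day and 1-day reminder messages", with no contrast exempted. Three exclusions follow:

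- "This robustness check will exclude patients who were randomized but were never sent messages for a variety of reasons", with inactive numbers and a do-not-contact list given as examples;
- "Additionally, we will exclude patients who were sent only a 3-day message, but who were not sent a 1-day message";
- people given duplicate texts through technical faults, described as few.

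Under Sample and Randomization, only groups 1-3 are messaged. Group 4 is described as "No additional contact beyond standard Geisinger flu shot communications". A patient sent the 3-day message misses the 1-day message if no longer on the day-prior eligibility list. That happens when the appointment was cancelled or moved to another day, or when a flu shot was recorded in the meantime.

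The primary outcome is "Flu vaccination at appointment [ Time Frame: 3 days after patient is randomized" in the SAP. In the Protocol (Detailed Study Procedures) it is vaccination at the scheduled appointment. Contrasts 1c (group 1 vs 4), 2 (group 3 vs 4) and 3b (group 2 vs 4) all use group 4; 1c and 2 are labelled confirmatory.

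**The concern.** The subset is defined by message records that group 4 cannot have. The SAP leaves two readings, and neither gives a usable check for 1c, 2 and 3b.

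- **Literal reading.** Nobody in group 4 received both messages, so the comparator is empty. Analysis 2 would have a predictor with a single level.
- **Group 4 kept whole.** This is an inference. The message arms lose patients because of events after randomisation, while the control keeps the same kinds of patients.

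Under the second reading, part of the filter is tied to the outcome. A patient who cancelled, moved to another day or was already vaccinated was not vaccinated at the originally scheduled visit. Dropping such patients from the message arms alone raises those arms' rate.

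Agreement or disagreement with intent-to-treat on these three contrasts could therefore come from the filter alone, and the check could not show whether those results are robust.

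**Working it through.** **The plan's own figure.** Two-sided 5%, 80% power, 50% vs 52%, pooled variance without continuity correction gives 9,806 per arm, and 4 x 9,806 = 39,224. Both match the SAP's Power analysis. The SAP does not state the significance level; two-sided 5% is inferred because it reproduces the figure exactly.

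**Inputs.** From the SAP: p = 50% (planning rate) and 9,806 per arm. p = 30% is added as an alternative. The rest are assumptions, because the documents give no values:

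- f = share of a message arm sent the 3-day but not the 1-day message;
- u = share never sent messages or sent repeats;
- q = vaccination rate in u.

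There is no true effect and group 4 is kept whole.

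**Step 1: missing 1-day message only, all such patients non-events.** Spurious difference = p/(1-f) - p = f*p/(1-f). For example, 0.02 x 0.50/0.98 = 0.0102.

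| f | p = 50% | p = 30% |
|---|---|---|
| 1% | +0.5 points | +0.3 |
| 2% | +1.0 | +0.6 |
| 5% | +2.6 | +1.6 |

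At p = 50%, the 2-point design effect is reached at f = 0.02/0.52 = 3.8%.

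**Step 2: all exclusions.** Spurious difference = (p - u*q)/(1-f-u) - p. Rejection is from a two-sided 5% z test with 9,806(1-f-u) vs 9,806 patients. At p = 50% and f = 2%:

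| u | q | Calculation | Difference | Rejection |
|---|---|---|---|---|
| 5% | 30% | 0.485/0.93 - 0.5 | +2.15 points | 84.1% |
| 5% | 50% | 0.475/0.93 - 0.5 | +1.08 | 31.5% |
| 5% | 70% | 0.465/0.93 - 0.5 | 0.00 | 5.0% |
| 10% | 30% | 0.470/0.88 - 0.5 | +3.41 | 99.6% |
| 10% | 50% | 0.450/0.88 - 0.5 | +1.14 | 33.7% |
| 10% | 70% | 0.430/0.88 - 0.5 | -1.14 | 33.7% |

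The bias is zero when q = p(1 + f/u): 0.5 x 1.4 = 70% at u = 5%, and 0.5 x 1.2 = 60% at u = 10%.

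**Step 3: if some patients without a 1-day message count as vaccinated.** This happens if any shot within 3 days counts. With a share e of f vaccinated, the component is (p - f*e)/(1-f) - p. At p = 50% and f = 5%: e = 0 gives +2.63 points, e = 25% gives +1.32, e = 50% gives 0.00 and e = 75% gives -1.32. The sign then depends on whether e is below or above p.

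**Step 4: alternatives under no effect.** 4,000 simulated trials, p = 50%, f = 2%, u = 5%, q = 30%:

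| Analysis | Mean difference | Rejection |
|---|---|---|
| Message arms filtered, group 4 whole | +2.16 points | 83.6% |
| Day-prior list applied to both arms | +0.01 | 5.9% |
| List in both arms plus delivery filter in message arm | +1.14 | 34.0% |
| Two-stage least squares | +0.01 | 5.5% |
| Intent-to-treat | +0.01 | 5.5% |

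At q = 70%, list plus delivery filter gives -1.01 points (28.6%), so a matched list rule does not rescue a one-sided delivery filter.

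**The case against.** The strongest reply is that the authors plainly meant delivery failures among patients assigned a message. Their examples of never-sent patients fit that, and deleting the whole control arm is an unlikely reading. This is fair, but it leads to the unstated alternative of keeping group 4 whole, where the arms are no longer comparable.

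A second point is that part of the filter could be matched. The SAP says "Each day, the study team receives a list of eligible patients with flu-shot-eligible appointments in the upcoming 3 days", without limiting the list by arm, so day-prior list status may exist for group 4. That stands as a possible repair. The SAP does not adopt it, and delivery and repeat messages have no group 4 counterpart.

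Third, even an at-appointment outcome could count a shot at a visit moved earlier within the 3-day window, so the upward component is certain only if the original appointment is meant. This stands, and Step 3 shows the effect.

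Fourth, every exclusion share is assumed, and the SAP itself calls the repeat-message group limited. This also stands: the rejection rates illustrate what the filter could do and do not estimate what it did.

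Finally, this is one supporting check and no decision rule depends on it. That limits the harm but does not make the check informative for 1c, 2 and 3b.

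**Conclusion.** The concern holds. As written, the both-messages check gives either no result or a non-comparable contrast for 1c, 2 and 3b. The net direction and size of the bias are unknown. Under the Step 2 assumptions the bias spans values from below zero to above the 2-point design effect. These figures rest on group 4 being kept whole and on assumed f, u and q.

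The consequence is confined to how this one check is read. The intent-to-treat results stand. Contrasts 1a, 1b and 3a apply one rule to both arms and are not part of this point, although they too condition on events after randomisation. The matter should be fixed, and confidence in the gap itself is high.

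**What to change.** State that the both-messages subset applies only to 1a, 1b and 3a. For 1c, 2 and 3b, choose one:

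1. **Drop this check.** Costs a change of SAP wording only.
2. **Use the day-prior list in all four arms**, if it covers group 4, with no delivery filter in groups 1-3. This needs group 4's list status. Say that list status is post-randomisation and delivery is unobserved in group 4. It is unbiased only if messages do not change who stays on the list.
3. **Two-stage least squares in all randomised patients**, with assignment as the instrument for delivery of at least the 3-day message. This needs one extra model. Its standard error is about 1/0.95 = 1.05 times intent-to-treat if 95% are delivered, and 1/0.90 = 1.11 times if 90% (assumed shares). Report it as an effect-of-receipt estimate: its test is nearly the same as intent-to-treat, and it targets the 3-day message rather than both.

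In every case, report exclusions by arm and reason. The SAP's Project status section says the primary-outcome data have already been extracted and analysed, so label the change as post hoc for that outcome.
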